5.6 Final study visit

At 12 months post randomisation, the patient will have a final study visit and the above tests performed. After this treatment allocation will be revealed and the patient will have the chance to decide whether they wish to continue receiving AV optimised His pacing. If they prefer not to decide the decision will be left to their direct medical care team.

The patient's GP and direct medical care team will be notified that the patient has completed the study and the patient will return to routine clinical care.

At the final study visit, participants will also be given the option of whether they would like to be contacted when the study results are available. They will be given the following options:

- Written communication of results
- Telephone call from research team
- Visit to discuss results with research team
- Meeting with direct medical care team to discuss results

Once patients have been informed of the study results they will be given the option of changing their choice of pacing treatment (1) Active treatment: His pacing with the AV delay programmed to the optimal sensed and paced delays identified during the optimisation process or 2) No His pacing treatment: device is programmed according to clinical indication). Should the patient want more time to consider this decision, further reviews or telephone communications could be scheduled.

5.7 Unblinding

Patients will be blinded to treatment arm. We anticipate that some patients may request a change in their treatment arm, particularly if there is a change in their symptom status. If this occurs we will try to encourage patients to continue with their designated treatment (either His pacing or no His pacing) until they cross over to the other treatment to complete

Confidential

the study. However, if they are not willing to continue treatment then their request for a change in treatment will be met. Our analysis will be made on an intention to treat basis. The master randomisation list will be stored electronically within a specialised 'blinded' folder in the statistics section of the Trial Master File (TMF) to ensure that the trial statistician does not have access to the list. A copy will also be made available to dedicated personnel in the research unit who will support unblinding of individual patient's treatment allocation upon request. Requests for unblinding should be discussed with the Chief Investigator or delegate beforehand.

6 TREATMENTS

6.1 Medical Devices

Medtronic CRT-D or CRT-P devices which meet the following criteria:

- 1. contains an IS1 port for the His lead (required)
- 2. contains a DF4 slot for the defibrillator lead (preferred)
- 3. certified MRI conditional

The His-bundle will be paced with a Medtronic SelectSecure 3830 69cm steroid eluting, bipolar, implantable, non-retractable screw-in catheter delivered transvenous pacemaker lead. The lead will be positioned using the C315 His delivery catheter, the SelectSite C304-L69/C304-S59 or other His delivery sheaths as per the implanting operator's discretion.

6.2 Labelling and Packaging

Refer to current manuals for the relevant product from the manufacturer.

6.3 Storage and Administration

Refer to current manuals for the relevant product from the manufacturer.

6.4 Monitoring Device Performance

Device data will be reviewed in person when patients attend for review at Visit 3, 4 and 5 (2 months, 8 months and 14 months post device implantation respectively). This will provide details on pacing thresholds, R wave amplitude and lead impedance. Details of any arrhythmia will also be seen. This data will be included in reports to the DMC for monitoring of any adverse consequences.

Device follow-up after cessation of the trial will be at the patient's local cardiology centre.

6.5 Device Precautions

Patients will be advised that prior to any future MRI scan or procedures that involve the use of diathermy, they should seek advice from their local pacing department so that their device settings can be adjusted to make the MRI/diathermy procedure safe and arrangements can be made to interrogate the device after the procedure.

6.6 Permanent Discontinuation of Study Treatment and Withdrawal from Study

(i) Permanent discontinuation of study treatment

Subjects may discontinue study treatment for the following reasons:

- At the request of the subject.
- Adverse event/ Serious Adverse Event
- If the investigator considers that a subject's health will be compromised due to adverse events or concomitant illness that develop after entering the study.

(ii) Withdrawal from Study

Withdrawal from the study refers to discontinuation of study treatment and study procedures and can occur for the following reasons:

- Subject decision
- Loss to follow-up

(iii) Procedures for Withdrawal from Study

If a patient wishes to withdraw from the study, they will be asked at what level they wish to withdraw i.e. if they would like to terminate pacing treatment but are willing to attend followup visits, or if they do not wish to be contacted about the study including results of the study. Reason for and level of withdrawal must be recorded in the eCRF and medical records. Patients will not be replaced and follow-up should continue if the patient agrees. In the event that a subject wishes to terminate treatment after implantation of the study device, the patient's GP or direct medical care team will be notified and the patient will return to routine clinical care.

7 ADVERSE EVENTS AND DEVICE VIGILANCE

7.1 Adverse Event (AE)

Any untoward medical occurrence, unintended disease or injury or any untoward clinical signs (including an abnormal laboratory finding) in subjects, users or other persons whether or not related to the medical device.

7.2 Adverse Event recording

All adverse events will be recorded using the InForm System with the following exceptions.

Exemptions:

All planned elective non-cardiac admissions/procedures/surgeries do not need to be reported as adverse events.

(i) Severity of Adverse Events

Confidential

HOPE-HF Sponsor: Imperial College (study ref: 15HH2828)

Mild: Awareness of event but easily tolerated

Moderate: Discomfort enough to cause some interference with usual activity

Severe: Inability to carry out usual activity

(ii) Causality of Adverse Events

Unrelated: No evidence of any causal relationship

- Unlikely: There is little evidence to suggest there is a causal relationship (e.g. the event did not occur within a reasonable time after administration of the medical device). There is another reasonable explanation for the event (e.g. the patient's clinical condition, other concomitant treatment).
- Possible: There is some evidence to suggest a causal relationship (e.g. because the event occurs within a reasonable time after administration of the medical device). However, the influence of other factors may have contributed to the event (e.g. the patient's clinical condition, other concomitant treatments).
- Probable: There is evidence to suggest a causal relationship and the influence of other factors are unlikely.

Definite: There is clear evidence to suggest a causal relationship and other possible contributing factors can be ruled out.

7.3 Serious Adverse Events (SAE)

i) Definition of SAE

An SAE is defined as any event that

- Results in death;
- Is life-threatening*;
- Requires hospitalisation or prolongation of existing inpatient's hospitalisation**;
- Results in persistent or significant disability or incapacity;
- Is a congenital abnormality or birth defect;

* "Life-threatening" in the definition of "serious" refers to an event in which the subject was at risk of death at the time of the event; it does not refer to an event which hypothetically might have caused death if it were more severe.

** "Hospitalisation" means any unexpected admission to a hospital department. It does not usually apply to scheduled admissions that were planned before study inclusion or visits to casualty (without admission).

Medical judgement should be exercised in deciding whether an adverse event/reaction is serious in other situations. Important adverse events/reactions that are not immediately life-threatening, or do not result in death or hospitalisation but may jeopardise a subject, or may require intervention to prevent one of the other outcomes listed in the definition above should also be considered serious.

(ii) Reporting of SAEs

All SAEs will be reported to the Sponsor within 24 hours of an Investigator becoming aware of the event. Reporting procedures are detailed in the study's SAE reporting instructions. If the investigator becomes aware of safety information that appears to be related to the

medical device or study procedures, involving a subject who participated in the study, even after an individual subject has completed the study, this should be reported to the Sponsor.

All SAEs will be reviewed by the Chief Investigator or a designated medically qualified representative to confirm expectedness and causality.

Expected AEs in this population of patients with Heart Failure will include hospitalisations related to arrhythmia, worsening shortness of breath and chest pain.

Reporting of SAEs and review by the CI will be via the trial data collection system (InForm).

7.4 Adverse Device Effects

Relatedness should be assessed in relation to both the medical device and to the procedures which are associated with the device function (e.g., insertion, removal).

Incidents related to the device will be reported to the Device Manufacturer (Medtronic) within 48 hours of the event happening to the designated Medtronic contact.

(i) Adverse Device Effects (ADE)

An ADE is defined as an AE related to the use of the medical device and includes any AEs resulting from insufficient or inadequate instructions for use, deployment, installation or operation, or any malfunction of the medical device (device deficiency). It also includes any AE resulting from user error or from intentional misuse of the medical device.

Anticipated Device adverse events are listed in the corresponding current device manual.

(ii) Serious Adverse Device Effect (SADE)

A SADE is an ADE that results in any of the consequences characteristic of an SAE.

(iii) Unanticipated Serious Adverse Device Effect (USADE)

Those SADEs which by nature, incidence, severity or outcome have not been identified in the current protocol or device brochure are considered an Unanticipated Serious Adverse Device Effect (USADE).

(iv) Anticipated Serious Adverse Device Effect (ASADE)

An ASADE is an effect which by nature, incidence, severity or outcome has been identified in the current device manual.

The Sponsor will be informed of all SADEs, either unanticipated or anticipated.

7.5 Reporting of Unexpected and Serious Adverse Events

Any SAE occurring to a study participant should be reported to the REC if in the opinion of the Chief Investigator the event was:

Related – that is, it resulted from administration of the medical device or any of the research procedures, and

Unexpected – that is, the type of event is not listed in the protocol/device manual as an expected occurrence and serious adverse events will be reported to the REC

Reporting of related and unexpected SAEs should be submitted within 15 days of the Chief Investigator becoming aware of the event.

Safety reports will be included in the annual progress report submitted to the Sponsor and the Ethics Committee.

8 STATISTICAL ANALYSES

8.1 Sample Size and power considerations

We will use a smoothed modified Bruce protocol for patients with heart failure. This enables improved reproducibility of peak VO₂³⁰. With this approach, reproducibility in heart failure patients between two separate visits to the hospital is 2.4 ml/kg/min, expressed as the standard deviation of the difference between two independent measurements³¹. Implantation of a cardiac resynchronisation therapy pacemaker in patients with broad QRS duration and heart failure results in a 0.5-2.5 (mean 1.5) ml/kg/min increase in peak VO₂³²⁻³⁷. Our published pilot data is that switching on classical cardiac resynchronisation therapy in patients with a broad QRS duration increments LV systolic blood pressure by ~10.3mmHg, and switching on direct His-bundle pacing in long-PR/narrow-QRS patients increment blood pressure by ~6.3mmHg, i.e. ~60% of that effect. Pro-rata we would therefore expect an estimated increment in peak VO2 of 60% of 1.5ml/kg/min, i.e. 0.9 ml/kg/min.

Adopting a conservative approach, a two-sided alpha of 0.05 is chosen. Using a paired ttest, in order to detect a difference of 0.7 with SD of 2.4, to achieve a power of 90% would require a total of 126 evaluable patients. Allowing for a combined mortality/dropout of 21%, the study would require a total sample size of 160 patients. Consequently, 160 patients will be randomised in a 1:1 manner to the treatment groups.

Detailed analysis methods will be documented in the study's Statistical Analysis Plan (SAP).

8.2 Data Analysis

Patient characteristics will be summarized. Summaries of continuous variables will be presented as means and standard deviations if normally distributed, and as medians and inter-quartile ranges for skewed data, whilst categorical variables will be presented as frequencies and percentages.

The analysis will be performed according to the intention to treat principle.

(i) Endpoint Analysis

The primary outcome will be analysed using a two-level hierarchal model. We will include treatment, period and sequence effect within the model. Random subject effects will also be included in the regression model if appropriate. Differences in secondary outcomes will also be analysed using aforementioned two level hierarchal model. Normality will be checked and appropriate transformation or non-parametric methods will be used if it is not met.

All statistical tests will be two-tailed with a 5% significance level.

A separate statistical analysis plan will be prepared and finalised prior to database lock.

(ii) Safety Analysis

Safety analysis will consist of descriptive statistics of fluoroscopy time at the time of device insertion, pacing thresholds, R wave amplitude, lead impedance, the frequency of lead malfunction, hospitalisations and death. This will be reviewed by the Data Monitoring Committee.

(iii) Economic evaluation

The analysis will be based on an intention-to-treat (ITT) principle. The comparability of the groups, in both costs and outcomes, will be examined by a baseline analysis. When both groups are not comparable methods will be applied to control for these differences. Normal distribution of the costs and effects will be tested by Kolmogorov-Smirnov test. When the normal distribution is not present, non-parametric bootstrapping will be performed to analyse the differences between the intervention and control group. The bootstrap method will be used to calculate the 95% confidence intervals (CI). The incremental cost-effectiveness ratio (ICER) will be based on the incremental costs and incremental effects of the intervention group and the control group and will be calculated as followed: ICER = $\Delta costs/\Delta$ effects. $\Delta costs$ and Δ effects are respectively the differences in costs and effects of the intervention and control group. Within the cost-effectiveness analysis the ICER will be expressed as costs per outcome rate and within the cost-utility analysis, the ICER will be expressed as the costs per QALY gain. A cost-effectiveness plane will be plotted with bootstrapped ICERs.

iv) Sub-group Analysis

- 1) Around 30% of patients (40 patients) recruited into the study are expected to have right bundle branch block. We will perform subgroup analysis to determine if the magnitude of haemodynamic response to AV optimised direct His bundle pacing is of a similar magnitude to that obtained in patients with narrow QRS duration.
- 2) We will perform analysis to determine whether a change in peak V0₂ and the haemodynamic response is related to baseline PR interval.
- 3) We will perform analysis to determine whether a change in peak VO2 and the haemodynamic response is related to E-A fusion as observed by baseline echocardiography.
- 4) We will perform analysis to determine the effect of AV delay optimised His Bundle pacing on daily activity level compared to control measured objectively in minutes per day by the CRT device.
- 5) If there are significant numbers of patients with non-selective His capture (where both the His and local ventricular myocardium are captured by the pacing stimulus) then we will perform subgroup analysis to determine whether there is a difference in the magnitude of either acute haemodynamic or change in peak V0₂.
- 6) If there are significant numbers of patients who are implanted with an LV lead due to the failure of His lead implantation we will perform subgroup analysis to determine whether there is a difference in their haemodynamic and peak VO2 response

compared to their control state and compared with the successful His implanted lead cohort.

- 7) A sub-group analysis will be performed to investigate patients recruited with a Ventricular Ejection Fraction of 35% and below against those recruited with an EF or greater than 35% for primary and secondary endpoints. Where possible, the analysis will be stratified by PR Interval in order to investigate whether PR is a predictor for treatment response.
- 8) It is anticipated that the vast majority of patients will have an indication for an implantable ICD. In the event where there is an even split between the two groups, an additional exploratory analysis may be carried out on the trial outcomes, using indication group as an additional stratification factor.
- 9) We will perform an analysis to assess the relationship between pacing device effect (in terms of change in peak VO2 and haemodynamic response) and BMI.

9 **REGULATORY, ETHICAL AND LEGAL ISSUES**

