3 STUDY DESIGN

3.1 Design

This is a multi-centre, prospective randomised double-blinded cross over study, recruiting a sub-population of patients with heart failure from multiple investigational sites in the UK. Recruitment is expected to take place over about 2 years.

All patients will be implanted with a Pacemaker or Implantable Cardioverter Defibrillator with one of the leads positioned on the His bundle in order to obtain His-bundle capture. There will be a 2-month run-in period where the device will be programmed not to deliver His pacing therapy during this period. Patients will be allocated in random order to six month treatment periods in each of the following two states (1) No His bundle pacing; (2) AV optimised Hisbundle pacing. Endpoint measurements will be taken at baseline, 6 months and 12 months post randomisation. Treatment allocation will be blinded to the endpoint assessor.

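### The primary model does not name the baseline peak VO2 that the trial collects; adding it is an optional, small gain confined to patients who complete only the first period

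*Protocol*

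**What the plan says.** Section 8.2(i) describes a two-level hierarchical model for peak VO2 and says: "We will include treatment, period and sequence effect within the model". Random subject effects are to be added only if judged appropriate. The same model serves the secondary outcomes.

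Section 3.1 says: "Endpoint measurements will be taken at baseline, 6 months and 12 months post randomisation". Appendix 2 agrees: cardiopulmonary exercise testing, echocardiography, BNP and the questionnaires are all marked at visit 3 (randomisation) as well as at visits 4 and 5.

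Section 8.1 plans for incomplete data: "Allowing for a combined mortality/dropout of 21%, the study would require a total sample size of 160 patients". It does not say when patients are expected to be lost. Sections 8.1 and 8.2 both refer to a separate SAP, which is not at hand.

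**The concern.** In a two-period crossover, a patient with both periods acts as their own control, and one pre-treatment value adds nothing to that comparison. A patient who leaves after period 1 has no second value. That patient informs the treatment effect only by comparison with other patients, and this comparison carries the full spread of fitness between patients. Baseline peak VO2 would remove most of that spread.

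The trial expects up to 34 of 160 patients to lack a pair and already pays for the baseline test. Leaving baseline out therefore forgoes some precision that needs no new data. What is at stake is a small amount of precision, not the validity of the primary analysis.

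**Working it through.** **The plan's own figures.** Inputs from section 8.1: difference 0.7, SD of the within-patient difference 2.4, two-sided alpha 0.05, power 90%.
- Normal approximation: (2.4 × (1.960 + 1.282) / 0.7)² = 123.5, so 124.
- Paired t-test (noncentral t): 126, with power 90.1%. This matches the protocol.
- Attrition: 126 / 0.79 = 159.5, so 160. This also matches. Non-completers: 160 − 126 = 34.

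**Set-up.**
- The 2.4 is "expressed as the standard deviation of the difference between two independent measurements", so the within-patient variance is w = 2.4² / 2 = 2.88 (SD 1.70).
- The between-patient SD is not in the protocol. I assume 2 to 6 ml/kg/min. The within-patient correlation is ρ = SD² / (SD² + 2.88), which runs from 0.58 to 0.93.
- Baseline is assumed to have the same variance, and the same correlation with later values, as the two outcome measurements.
- There are 126 completers and m patients with a period-1 value only, split equally between sequences. Let f = m / (126 + m).

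**Formula.** With treatment, period, sequence and a random patient effect, generalised least squares gives

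Var(treatment effect) = (2.4² / 126) × [1 − (w / 2V) × f],

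where V is the variance of a single period-1 value.
- Without baseline, V = w / (1 − ρ), so the bracket is 1 − f(1 − ρ)/2.
- With baseline, V = w(1 + ρ), so the bracket is 1 − f / (2(1 + ρ)).

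With m = 0 the bracket is 1 in both cases. The SE is 2.4 / √126 = 0.2138 with or without baseline, so completers gain nothing.

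**Worked case, SD 4, m = 34.** ρ = 16 / 18.88 = 0.847 and f = 34 / 160 = 0.2125.
- Without baseline: bracket = 1 − 0.2125 × 0.153 / 2 = 0.984, SE 0.2121.
- With baseline: bracket = 1 − 0.2125 / (2 × 1.847) = 0.942, SE 0.2076.
- Variance reduction: 1 − 0.9425 / 0.9838 = 4.2%.

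**Upper limit, m = 34** (power by normal approximation):

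| Between-patient SD | ρ | SE without | SE with | Variance reduction | Power without → with |
|---|---|---|---|---|---|
| 2 | 0.58 | 0.2090 | 0.2065 | 2.4% | 91.8% → 92.4% |
| 4 | 0.85 | 0.2121 | 0.2076 | 4.2% | 91.0% → 92.1% |
| 6 | 0.93 | 0.2130 | 0.2078 | 4.8% | 90.8% → 92.1% |

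**Fewer one-period patients** (variance reduction at SD 2, 4 and 6):
- m = 10: 0.8%, 1.4%, 1.6%.
- m = 20: 1.5%, 2.7%, 3.1%.

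**In completer equivalents** (126 / bracket − 126). The 34 one-period patients are worth 5.9, 2.1 or 1.0 completers without baseline, and 9.1, 7.7 or 7.4 with it. The gain from baseline is therefore about 3 to 6 completers. With m = 20 it is about 2 to 4.

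**How much the model already recovers.** The ratio of the two variance savings is 1 − ρ²: 66% at SD 2, 28% at SD 4 and 14% at SD 6.

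**The case against.** The strongest objection is that nothing here is wrong. Treatment, period and sequence with a patient level is a standard model for this design. The list of terms does not forbid a covariate, and details are deferred to the SAP. All of that stands, and it is why this is an optional improvement. The point is still worth making because the protocol goes beyond silence: it names its terms, and an SAP author could carry the list forward as it is.

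A reader might infer that the plan throws away the data of a fifth of its patients, or that its power is at risk. The protocol supports neither reading.
- The 126 and 160 reproduce without using one-period patients or baseline.
- The 21% combines deaths and drop-outs at any time. Patients lost before 6 months have no outcome for baseline to help, so 34 is a ceiling.
- With a random patient effect, one-period patients already contribute something without baseline.

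A reader might also argue that baseline makes the missing-at-random assumption more credible. That is reasonable in general, but the protocol does not link drop-out to baseline fitness. For patients who leave after period 1, a likelihood-based model already conditions on the 6-month value. I put no weight on this argument.

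Two further objections change the fix. First, the gain needs a random patient effect, which section 8.2(i) makes conditional; with fixed patient effects a one-period patient adds nothing, with or without baseline. Second, a plain covariate drops any patient whose visit 3 test is missing. Losing about 2 to 4 complete pairs would cancel the gain from 20 one-period patients, and about 3 to 6 would cancel that from 34.

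**Conclusion.** The point holds as a minor, optional efficiency gain. Baseline peak VO2 is collected and is not among the named model terms. Adding it does nothing for complete pairs and at best raises power by 0.6 to 1.3 points, when all 34 non-completers have a 6-month value. With 10 to 20 such patients the variance falls by 0.8% to 3.1%. The planned 90% power stands either way.

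The size rests on three assumptions that the protocol does not settle: a between-patient SD of 2 to 6 ml/kg/min, a baseline that correlates with each outcome as strongly as the outcomes correlate with each other, and the number of patients lost after rather than before the 6-month visit. No gain has been calculated for the secondary outcomes. The same reasoning applies to those with a baseline, but the size is unknown.

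**What to change.** In section 8.2(i), or in the SAP before database lock, state that:
- the visit 3 value of the outcome enters the two-level model as a fixed covariate, for each outcome that has one;
- the random patient effect is retained, without the present condition;
- patients with one post-randomisation measurement stay in the analysis;
- missing baselines are handled so that no complete pair is dropped, for example by simple imputation of the baseline or by modelling it as a further response.

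The cost is a few sentences and no new data. The only downside is that the missing-baseline rule becomes necessary and must be fixed in advance.

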5.5 Study assessments

Physical examination

Patients will have a physical examination where vital signs will be taken.

Cardiopulmonary exercise testing:

Patients will exercise on a treadmill using a "smoothed modified Bruce" protocol ³⁰. A physiologist and another HOPE HF study team member (e.g. research nurse, research fellow or another physiologist) will be present for this test. For safety reasons, it is necessary to perform ECG monitoring during this test. It may be possible to see pacing spikes in the ECG. Therefore to ensure that the physiologist who is leading the exercise test is blinded, the screen displaying the ECG will only be visible to the second study personnel who will be responsible for monitoring ECG. They will only request that a test is stopped if there are ECG findings which make this necessary on clinical safety grounds. This way both the patient and the physiologist leading the exercise test will remain blinded to the treatment arm. Exercise capacity will be measured as peak exercise oxygen consumption in ml/kg/min.

BNP:

We will take 5mls of blood to measure B type Natriuretic Peptide (BNP) in an EDTA bottle. The samples will be analysed at the Hammersmith hospital and no sample will be stored.

Echocardiography:

Patients will have a standard HOPE HF echo protocol performed including left ventricular dimensions, volumes, ejection fraction and quantification of mitral regurgitation. No ECG will be recorded during the echocardiogram once the patient is randomised. The physiologist performing the test will be blinded to the treatment arm.

Daily Activity Measurement:

All implanted devices in the study can provide data on daily activity measured in minutes per day. The comparison will be made between the His pacing and no His pacing arms.

Quality of Life (QOL) and Cost Effectiveness Evaluation questionnaires:

The economic evaluation will compare incremental costs and incremental outcomes of the direct His-bundle pacing against standard medical care. The economic evaluation will consist of two parts, a cost-effectiveness analysis (CEA) and a cost utility analysis (CUA). In the CEA the incremental cost-effectiveness ratio (ICER) will be expressed as the incremental costs per point improvement in exercise capacity in peak VO₂. The primary outcome measure in the CUA will be Qualitative Adjusted Life Years (QALYs), based on the EuroQoL EQ-5D scores.

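### Section 8.2(iii) words the economic evaluation of this crossover as a parallel-group comparison, and its ICER does not match the comparator named in section 5.5

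*Protocol*

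**What the plan says.** **Design.** Protocol section 3.1: "Patients will be allocated in random order to six month treatment periods in each of the following two states", namely His pacing off and AV-optimised His pacing. Section 5.4 has each patient change to the other state after six months. On devices, section 3.1 says: "All patients will be implanted with a Pacemaker or Implantable Cardioverter Defibrillator with one of the leads positioned on the His bundle". Appendix 2 places the implant two months before randomisation. It schedules the resource-use questionnaire at visits 1, 3, 4 and 5, and the other questionnaires and the exercise test at visits 3, 4 and 5.

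**Economic analysis, section 8.2(iii).** "The comparability of the groups, in both costs and outcomes, will be examined by a baseline analysis". The next sentence is: "When both groups are not comparable methods will be applied to control for these differences". If costs or effects are not normally distributed, "non-parametric bootstrapping will be performed to analyse the differences between the intervention and control group". The ICER is the difference in costs over the difference in effects between those two groups.

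**Other outcomes, section 8.2(i).** The primary model has treatment, period and sequence. "Differences in secondary outcomes will also be analysed using aforementioned two level hierarchal model". Section 2.4 lists cost effectiveness as secondary endpoint 5. Section 8.2(i) also provides: "Normality will be checked and appropriate transformation or non-parametric methods will be used if it is not met".

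**Comparator, section 5.5.** "The economic evaluation will compare incremental costs and incremental outcomes of the direct His-bundle pacing against standard medical care".

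**The concern.** A baseline check followed by adjustment suits a trial in which different patients form the two arms. Here the contrast behind the ICER is between two states of the same patients. Taken as written, the check compares a set of patients largely with itself, and the adjustment has little to act on. An analyst who sees this must then decide what was meant, possibly after seeing the data. Section 8.2(i) already has a suitable structure for secondary outcomes, but 8.2(iii) describes a group contrast instead.

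The comparator matters more for interpretation. An ICER labelled as against standard medical care will be read as including the cost of giving patients the device. The quantity defined in 8.2(iii) does not include it.

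**Working it through.** The economic section gives no sample size, power or cost figure, so there is no economic figure to reproduce. The trial-level figures used below do reproduce. A paired t-test with difference 0.7, SD 2.4 and two-sided alpha 0.05 needs 126 patients (power 90.1%), and 126 / (1 − 0.21) = 159.5, rounded up to 160.

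**1. Baseline difference between states, complete patients.** Let b be a patient's pre-randomisation value: resource use at visits 1 and 3, or other questionnaires and exercise test at visit 3. The same b belongs to the on state and the off state, so b(on) − b(off) = 0 for each patient, and the mean over any set of such patients is 0. The month-6 visit is not a second untreated baseline, because it follows six months in the first state.

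**2. Where the check has content.**
- *Between sequences.* 160 / 2 = 80 patients per sequence. These are different patients, so a baseline comparison is meaningful. It is not the contrast that enters the ICER.
- *Through one-period patients.* Suppose m patients give both periods, k give only the on period and k give only the off period. The baseline mean difference between states is then k / (m + k) times the difference between the on-only and off-only patients. The plan allows 160 − 126 = 34 losses. If all 34 left after period 1 and split evenly (an assumption), k = 17, m = 126 and 17 / 143 = 0.12. The check would then see about one eighth of any imbalance among the patients who left.

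**3. Analysis structure.** Section 8.2(i) puts secondary outcomes under the treatment, period and sequence model, and 2.4 makes cost effectiveness one of them. Section 8.2(iii) mentions neither period nor sequence and speaks of two groups. The bootstrap itself is no conflict, since 8.2(i) allows non-parametric methods.

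**4. Comparator.** Let I be the implant cost, incurred before both periods, and c the cost within a period.
- On versus off, as 8.2(iii) defines it: (I + c_on) − (I + c_off) = c_on − c_off. The implant cost cancels.
- Against care without the study device: (I − D) + (c_on − c_care), where D is the cost of any device the patient would have had anyway. The implant cost stays unless D equals I.

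The ICERs differ by (I − D) / effect, if the off state otherwise stands in for standard care. As a scale only, each 1,000 currency units of I − D adds 1,000 / 0.7 = 1,429 per ml/kg/min at the design difference of 0.7, or 1,000 / 0.9 = 1,111 at the expected 0.9. The protocol gives neither I nor D, so the actual gap is unknown. Section 8.2(iv) expects most patients to have an ICD indication. For those who would receive an ICD anyway, I − D may be small.

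**The case against.** The protocol uses the word group loosely. Section 8.1 randomises patients to treatment groups and section 5.4 randomises them to active or no His pacing, so at visit 3 the groups in existence are the two randomised allocations. A baseline check between those is ordinary. This is a fair reading of the baseline sentences taken alone. It does not carry through the paragraph, because 8.2(iii) goes on to form the ICER between an intervention and a control group without separating the two meanings.

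A reader might infer that the check cannot apply at all. The documents do not support that: the sequence comparison is meaningful, and up to 34 of 160 patients may be lost, so the two states need not contain exactly the same patients.

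A reader might also infer that the bootstrap treats the states as independent samples and gives confidence intervals that are too wide. Section 8.2(iii) does not say so. The resampling unit is a detail that can be left to the SAP, which was not available here, so no such inflation is claimed.

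Finally, standard medical care in section 5.5 may be a loose label for the off state; the same section compares His pacing with no His pacing for daily activity. That is possible. If so, the label still needs correcting, because the two readings define different ICERs.

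**Conclusion.** The point holds as a minor inconsistency in a secondary economic analysis. The baseline rule in 8.2(iii) does not fit the crossover: it is uninformative for patients with both periods and retains content only between sequences or through one-period patients. The ICER defined there is on versus off in implanted patients, so it cannot be read as an ICER against care without the study device, which is the natural reading of section 5.5. The numerical gap cannot be derived from the protocol.

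The zero baseline difference assumes complete patients and pre-randomisation records as the baseline. The cancellation of the implant cost follows from the timing of the implant. The primary analysis and the sample size of 126 evaluable and 160 randomised patients do not change.

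**What to change.** In section 8.2(iii):
- define incremental costs and effects as within-patient on-minus-off differences, accounting for period and sequence as in 8.2(i);
- state that any bootstrap resamples whole patients;
- limit the baseline comparability check to the two randomised sequences.

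In 5.5 and 8.2(iii) together, state one comparator. It is either pacing on versus off in implanted patients, or standard medical care with the implant cost added explicitly. The second option should also say how patients who would receive an ICD anyway are costed, and that the off state stands in for standard care in other respects.

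The cost is a text edit and analysis code. The questionnaires and exercise test needed for the on-minus-off analysis are already scheduled. An implant unit cost is needed only if standard medical care is kept as the comparator.
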